implementation and scalability of the intervention including nurse involvement. Nurses concurred with pts experiences, and suggested strategies to recruit and retain dyads for the study, which are now included in the methodology section of the current grant proposal. Studies 3.6 and 3.7 represent the building blocks for the development of our Recovering Together program and manual. Nurses provided edits and contributed to the iterative development of the manual. These studies also confirm feasibility of conducting the pilot RCT proposed through this R21.

II. SPECIFIC AIMS

The current study has the following objectives:

Aim 1: To determine the feasibility of recruitment, feasibility of program delivery, program credibility, and program satisfaction using evidence-based benchmarks.

Hypothesis 1: We hypothesize that > 75% of the dyads approached will agree to participate.

Hypothesis 2: We hypothesize that > 75% of dyads who start the intervention will complete at least 4 sessions.

Hypothesis 3: We hypothesize that > 75% of participants will report average credibility (Credibility and Expectancy Questionnaire) scores greater than the scale's midpoint.

Hypothesis 4: We hypothesize that > 75% participants will report average satisfaction (Client Satisfaction Scale) scores greater than the scale's midpoint.

Aim 2: To demonstrate a proof of concept that the Recovering Together program can sustainably improve emotional distress [Hospital Anxiety and Depression Scale; HADS], Post Traumatic Symptoms (PTS) [PCL-S], resiliency variables (mindfulness, coping, social support and self-efficacy) and interpersonal factors (interpersonal bond).

Hypothesis 1: We hypothesize that participation in the Recovering Together Program will be associated with a more potent decrease in emotional distress and PTS compared to participation in the educational program (control), and that these improvements will maintain at 3 month follow up.

Hypothesis 2: We hypothesize that Recovering Together Program will be associated with a more potent increase in resiliency variables (mindfulness, coping, social support, self-efficacy) and interpersonal factors (interpersonal bond) compared to participation in the educational program, and that these improvements will maintain at 3 month follow up.

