their head, etc. The means by which consent was given by the subject will be documented in the consent form and research record. If cgs cannot be reached in person in the hospital, they will be contacted via phone to complete informed consent. Cgs will be given a copy of the consent form to review while discussing the study over the telephone. We will fax or securely e-mail the consent form prior to obtaining consent. Cgs will return a signed copy of the consent form. After the document has been reviewed, study staff will answer any and all questions the pt or cg may have. Once all questions have been addressed, each member of the dyad will sign the consent form, which will include a description of all study procedures, the option to receive text message reminders, information about potential risks and benefits of participation, and study contact information (including that of the IRB) in case questions arise at a later time. The consent form will also explicitly state that study participation is voluntary, and that participants may refuse to answer any questions that make them uncomfortable, and may discontinue participation at any time. In addition, participants will be assured that withdrawal from the study will not compromise their medical care in any way.

As informed consent is a continuous process, participants will be given a copy of the signed informed consent document, and will be invited to ask questions about their participation at any point over the course of the study.

Following a study enrollment and baseline assessment, dyads will be randomly assigned to either the newly developed psychosocial intervention or to the educational program (control) using a random number sequence generator to ensure comparability between groups. We will document time between assessment and intervention initiation, and analyze as a predictor of study outcomes as needed. Randomization will be developed by the statistician, without any input from the rest of the team.

V. STUDY PROCEDURES

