After enrollment, participants will complete study assessments. All subjects will be given baseline psychological and behavioral assessments that will assess depression, anxiety, PTS symptoms, and other psychological constructs. Assessments will be administered online, using the REDCap system. Subjects may choose to fill out these questionnaires on-site, or to fill them out at home on a personal computer or other Internet-equipped device. This assessment includes demographic information and a battery of psychological questionnaires. We will also collect information about important clinical variables including duration of acute hospitalization. All questionnaires are itemized below:

Administered at Baseline Only:

Demographics

Prior Mental Health History questions

Credibility Questionnaire

Administered at Baseline, Post-Intervention, and Follow-up:

Medical history information from LMR (i.e., prior ANI status, current psychotropic meds, comorbid medical conditions, etc.)

Post-Traumatic Stress Disorder Checklist (PCL-S)²⁹

Hospital Depression and Anxiety Scale (HADS)³⁰
 Measure of Current Status Part A (MOCS-A)³¹
 The Cognitive and Affective Mindfulness Scale (CAMS)³²
 World Health Organization Quality of Life (WHOQOL-BREF)³³
 Dyadic Relationship Scale (DRS)
 Experience in Close Relationships – Relationship Structure (ECR-RS)

Administered Post-Intervention and Follow-up Only:
 Client Satisfaction Questionnaire (CSQ-3)³⁴

The study staff will complete the following questionnaires to assess symptom severity for each patient at all 3 timepoints (baseline, post intervention and follow up):

Modified Rankin Scale (mRS)³⁵ [Pts only]
 Barthel Index³⁶ [Pts only]

After completing the baseline assessments, dyads will be randomized to either the newly developed psychosocial intervention or to treatment as usual.

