current care. This may include meeting with nurses, physical therapists, medical doctors, and other members of the pt's medical team. Treatment as usual may also involve administration of SSRI to those patients with motor problems.

Participants in both groups will be given post-treatment psychological and behavioral assessments identical to those administered at baseline, in addition to the CSQ-3. As a baseline, participants will be given the option to complete post-treatment questionnaires on site or at home. Participants will be asked to complete questionnaires immediately after completion of the group intervention (T2), and 3 months (T3) after completion of the group intervention, in order to measure long term outcomes. Study staff will email these questionnaires to the participants via the REDCap system or give participants the option to complete them over the phone with a study staff member.

VI. BIOSTATISTIC ANALYSIS

We plan to conduct a RCT with patients from the Neuro-ICU. The main intervention goal is to provide dyads with resiliency and interpersonal communication skills necessary to optimize recovery. Dyads will be medically cleared by a member of the nursing staff. Nurses will then screen dyads for exclusionary cognitive criteria. Dyads will complete additional screening and baseline questionnaires with a trained research assistant. Dyads will be randomized to one of two groups 1) Psychosocial skills based intervention (Recovering Together), or 2) Educational Control.

We chose our study measures based on our theoretical frameworks, strong psychometric properties in studies of patients with ANI, and feasibility in our prior work with ANI dyads. Measures will be collected at baseline, post-intervention, and at 3 month follow up. Data collection and management will be conducted with Research Electronic Data Capture. Dyads will be given the option to complete measures electronically, by paper and pencil, or telephone.

1) Is the psychosocial skills-based intervention feasible, credible usable, and accepted by pts and cgs in the ICU?

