[name] developed the proposed study design in collaboration with the NICU study team (nurses, physicians, clinical interns) and an MGH psychologist who specializes in using mindfulness and emotion regulation in both chronic illness and medically healthy populations. With funding from the American Heart Association, we conducted 20 qualitative interviews with pt-cg stroke dyads at risk for chronic emotional distress during NICU hospitalization. We also conducted additional clinical interviews with 10 pt-cg dyads representative of other ANI diagnoses. 83% of dyads approached agreed to participate. Pts (23) and cgs (25) were mostly women. Dyads were mostly spouses and mothers-daughter. Dyads noted interest in a resiliency program (30/30) and preferred a combination of in person and live video sessions (30/30). Dyads learned about resiliency skills (name, description, and goal) and agreed they would be helpful to them. They also noted interest in learning about: survivorship plans, adaptation to deficits (present or anticipated), and return to normal living. This led to the development and subsequent refinement (through feedback from the nursing team) of the Recovering Together Program active intervention.

3) Is the effect of the skills-based intervention for pts and cgs in the ICU durable?

We will assess feasibility, usability, and acceptability by the enrollment numbers, participants completion in at least 4 out of 6 sessions, and the questionnaires, The Credibility and Expectancy and Client Satisfaction Scale. These will be primary outcomes. The PCL-S, HADS, and resiliency measures will serve as the secondary outcomes.

We will use student's t-test to assess within-group differences in long-term outcomes. We will compare measures at the 3 month follow-up assessment to measures at the post-intervention assessment for both study arms.

We will also use t tests and chi squared tests to assess differences at the 3 month follow up.

VII. RISKS AND DISCOMFORTS

There is a risk that some participants may feel uncomfortable completing various psychological questionnaires or parts of the skills-based on intervention. Participants are free to withdraw from the study at any time, as the study is completely voluntary.

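### The only stated between-arm test of the distress and resiliency outcomes appears to leave out the pre-randomisation baseline score, which costs precision in the effect estimates the pilot is meant to supply

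*Combined protocol and SAP*

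**What the plan says.** Section II, Aim 2, Hypothesis 1 predicts that the intervention "will be associated with a more potent decrease in emotional distress and PTS compared to participation in the educational program (control" arm), with the improvement kept at 3 months.

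Section V lists the PCL-S, HADS, MOCS-A, CAMS and the relationship scales under the heading "Administered at Baseline, Post-Intervention, and Follow-up", and Section VI confirms the schedule: "Measures will be collected at baseline, post-intervention, and at 3 month follow up". Section IV places the baseline before allocation: "Following a study enrollment and baseline assessment, dyads will be randomly assigned". Each randomised participant should therefore have a baseline score that allocation cannot have influenced.

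Section VI, question 3, states two analyses of these outcomes. One is a within-group t-test: "We will compare measures at the 3 month follow-up assessment to measures at the post-intervention assessment for both study arms". The other is "We will also use t tests and chi squared tests to assess differences at the 3 month follow up". Question 2, on effectiveness, names no test; the text beneath it describes how the programme was developed.

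The only possible covariate named is in Section IV: "We will document time between assessment and intervention initiation, and analyze as a predictor of study outcomes as needed". No baseline-adjusted model, change score or repeated-measures model is planned. The actor-partner model appears in Section I as theory, not as an analysis.

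**The concern.** A hypothesis about a greater decrease refers to where participants started, but neither stated test uses the starting value. If the 3-month comparison is of scores at that visit alone, all between-person variation that baseline could explain stays in the error term. Any chance difference between the arms at baseline is also carried in part into the estimated effect.

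This matters because Section VI gives estimating effect sizes for distress as one purpose of the sample, and discusses their use in later sample-size calculations. With about 30 dyads per arm those estimates will be imprecise, and the covariate that could sharpen them is already being collected. Section IV mentions no stratification on baseline distress, so any balancing has to come from the analysis.

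**Working it through.** **Inputs from Section VI.** 40 dyads per arm recruited, attrition of 25%, 30 dyads per arm left. The plan's own figure reproduces: 30 / (1 − 0.25) = 40.

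**Assumptions, because the documents give no values.** Two-sided alpha 0.05; 80% power; effects in SD units with equal SD at baseline and follow-up; patients and caregivers analysed separately, so n = 30 per arm; correlation r between baseline and follow-up from 0.2 to 0.7. Low values are included because baseline is taken during acute hospitalisation.

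**Unadjusted comparison.** The SE of the arm difference is √(2/30) = 0.258 SD, and the 95% CI half-width is 1.96 × 0.258 = 0.51 SD. The two-sample t-test detects 0.736 SD with 80% power.

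**Baseline as covariate.** The SE is multiplied by √(1 − r²). The detectable difference is 0.736 × √(1 − r²), and the equivalent unadjusted sample is 30 / (1 − r²) per arm.

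**Change score.** The SE is √(4(1 − r)/30), which is the unadjusted SE times √(2(1 − r)). That factor exceeds 1 whenever r is below 0.5.

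| r | √(1 − r²) | Detectable difference, adjusted (SD) | Equivalent n per arm | CI half-width, adjusted (SD) | CI half-width, change score (SD) |
|---|---|---|---|---|---|
| 0.2 | 0.980 | 0.72 | 31 | 0.50 | 0.64 |
| 0.3 | 0.954 | 0.70 | 33 | 0.48 | 0.60 |
| 0.4 | 0.917 | 0.67 | 36 | 0.46 | 0.55 |
| 0.5 | 0.866 | 0.64 | 40 | 0.44 | 0.51 |
| 0.6 | 0.800 | 0.59 | 47 | 0.40 | 0.45 |
| 0.7 | 0.714 | 0.53 | 59 | 0.36 | 0.39 |

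The adjusted figures ignore the small cost of estimating the baseline slope, so at r = 0.2 there is almost nothing to gain.

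**Chance imbalance.** The baseline difference between arms also has SE 0.258 SD. A gap of 0.3 SD or more has z = 0.3 / 0.258 = 1.16 and probability 0.245; a gap of 0.5 SD or more has probability 0.053. A fraction r of the gap passes into the raw 3-month difference, so a 0.3 SD gap shifts it by 0.09, 0.15 or 0.21 SD at r = 0.3, 0.5 or 0.7.

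**Effect on false positives, given the gap.** With no true effect and a baseline gap b, the unadjusted z statistic is normal with mean r·b / 0.258 and SD √(1 − r²). At r = 0.3, 0.5 and 0.7 the chance of exceeding 1.96 in absolute value is 5.3%, 5.7% and 5.4% for b = 0.3 SD, and 8%, 13% and 20% for b = 0.5 SD. A moderate gap hardly matters for the test; a large and rare one does.

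**The case against.** The strongest reply is that nothing here is invalid. Randomisation makes the unadjusted t-test unbiased on average with correct overall type I error, and its standard error already allows for chance imbalance. A reader might infer that the planned comparison is biased, or that a baseline imbalance will routinely be taken for an effect. The documents and the arithmetic do not support that: a 0.15 SD shift sits inside a CI half-width of 0.51 SD. Nor are precision and imbalance two separate benefits, since the variance that adjustment removes includes the part carried by the baseline difference. All of this stands.

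Section VI also does not say that the 3-month tests use raw scores, or even that they compare arms. That is the plain reading, and nothing in the documents supports an adjusted one, but it remains an inference. Nor is this the only test stated at 3 months, because the within-group comparison is another. That test does not use baseline either, so the point survives.

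The gain depends on a correlation the documents do not give. It is tempting to argue that the entry rule, which needs only one distressed member per dyad, guarantees widely spread baseline scores and hence a large gain. No baseline data are given, and the gain depends on r, not on spread alone.

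Finally, the sample was sized for feasibility and stable means and SDs, with no power target. That limits the weight of the point. It does not remove it, because Section VI also asks for distress effect sizes and calls them its primary quantitative outcomes.

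**Conclusion.** The concern holds as a recommendation to improve efficiency and specify the analysis, not as a flaw that invalidates the trial. On its plain reading the only stated between-arm analysis leaves out a baseline score that the trial will hold for its randomised participants.

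Under the stated assumptions, using baseline is worth between almost nothing (r = 0.2) and the equivalent of 59 instead of 30 per arm (r = 0.7). At r = 0.5 it matches the precision of 40 per arm, the number recruited before attrition. The figure of 30 assumes one role at a time. Section VI also counts 60 participants per arm, but the two members of a dyad are not independent, so those 60 cannot be treated as separate observations.

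These outcomes are listed as secondary in Section II and under question 3, and the Aim 1 benchmarks are untouched. The change should be made, but nothing about the feasibility conclusions depends on it.

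**What to change.** In Section VI, state that each continuous outcome will be analysed post-intervention (T2) and at 3 months (T3) with the participant's own baseline score as covariate, by ANCOVA at each time or a repeated-measures model over both. Fit it separately for patients and caregivers, or allow for dyad clustering if they are pooled. Report the adjusted arm difference with its 95% CI as the effect size. Naming the T2 analysis also supplies a test for question 2, which has none.

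Do not substitute a t-test on change scores: below r = 0.5 it is less precise than the unadjusted comparison.

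Leave adjustment of binary outcomes optional. Logistic adjustment changes the odds ratio from a marginal to a conditional one and does not shrink its standard error as ANCOVA does, so the plan should say which is reported.

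The cost is a few sentences and a slightly longer model specification. No new data, visits or recruitment are needed.
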